Intervention Women will be randomized for ovarian stimulation with letrozole or to natural cycle IUI. In the group allocated to ovarian stimulation, women will receive oral tablets letrozole 5 mg daily from cycle day 3-5 for 5 days. We will treat the couples for 3 cycles, with a time horizon of 4 months.

Main study parameters/endpoints

Primary outcome is ongoing pregnancy leading to live birth. Secondary endpoints are clinical pregnancy, multiple pregnancy, miscarriage rates, pregnancy complications and patients' costs.

Nature and extent of the burden and risks associated with participation, benefit and group relatedness

The strategies compared are already broadly applied in current practice. No additional risks are expected. There is no benefit for participants, but the results may benefit future subfertile couples

1. INTRODUCTION AND RATIONALE

In many areas around the world, intrauterine insemination (IUI) is the treatment of first choice for couples with unexplained and mild male factor infertility due to its simplicity, ease of management, and relatively low cost(1)(2). While IUI can be applied in the natural cycle, in many settings ovarian stimulation is applied with the aim to establish multiple follicular growth. Multiple follicular growth is thought to increase the chances of pregnancy and live birth, but bears at the same time the risk of multiple pregnancy (3). It is therefore controversial whether ovarian stimulation improves fertility outcomes to the couples without female ovulation disorders in an IUI program(4,5). Various stimulation protocols have been applied, but there is still no consensus on the optimal protocol for ovarian stimulation in an IUI program (6,7). We found in a retrospective cohort study that ovarian stimulation with letrozole significantly increases the live birth rate as compared to natural cycle IUI without substantially increasing the multiple pregnancy rate in IUI program for unexplained and mild male factor infertility. Also, letrozole was found to result in similar pregnancy and live birth rates for a lower multiple pregnancy rate than Clomid or letrozole.

We therefore plan to perform a randomized clinical trial (RCT) on the women with unexplained and mild male factor infertility in IUI program in Centre of Reproductive Medicine, Peking University Third Hospital, Beijing, China. We aim to test the hypothesis that in couples with unexplained or mild male factor infertility scheduled for an IUI program ovarian stimulation with letrozole increases the live birth rate as compared to natural cycle treatment.

2. OBJECTIVES

Primary Objective:

To test the hypothesis that that in couples with unexplained or mild male factor infertility scheduled for an IUI program ovarian stimulation with letrozole increases the live birth rates over IUI in the natural cycle

We aim to answer the following questions:

What are after 3 cycles of IUI with letrozole and IUI in natural cycle;

- live birth rates
- multiple pregnancy rates
- financial costs

3. STUDY DESIGN

Study design

A randomized clinical trial comparing 3 cycles of IUI with letrozole to 3 cycles of IUI in natural cycle within a time horizon of 4 months.

Time schedule

We aim to include 100 women. A total of 14 months will be needed; 1 month preparation, 5 months inclusion, 4 months treatment, 3 months follow up and 1 months analysis/report writing.

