4.4 Sample size calculation

Our sample size is based on an cumulative live birth rate. We anticipate an 18% pregnancy rate after 3 cycles natural cycle IUI. We presume that the clinical relevant difference is 8%. To test the hypothesis that IUI with letrozole increased the pregnancy rate to 26% as compared to natural cycle IUI, we need to include 483 women per arm (total 966). (two sided-test, alpha .05, beta .80, 15% loss to follow-up). Firstly we will collect 100 women for a pilot study.

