6.2 Randomisation, blinding and treatment allocation

Randomization will be performed centrally with the use of envelope method.

The study will be completed 4 months after randomisation, with a maximum of 3 cycle attempts. According to local protocol, participants may be offered more IUI cycles, with medication to their preference after the 4 months study period, or proceed to IVF immediately.

The study will be open.

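### The 100 women who are scheduled do not carry the stated 80% power, and the 966 who do have no schedule: Sections 3, 4.4 and 8 need reconciling

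*Combined protocol and SAP*

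**What the plan says.** Section 3 (Time schedule) states "We aim to include 100 women" and adds the only timetable for the trial as a whole: "A total of 14 months will be needed; 1 month preparation, 5 months inclusion, 4 months treatment", then 3 months of follow-up and 1 month for analysis and reporting. The word pilot does not appear there.

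Section 4.4 gives another number for the hypothesis test. It writes "To test the hypothesis that IUI with letrozole increased the pregnancy rate to 26% as compared to natural cycle IUI" and continues "we need to include 483 women per arm (total 966", with the settings "two sided-test, alpha .05, beta .80, 15% loss to follow-up". It ends: "Firstly we will collect 100 women for a pilot study".

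Section 2 has one primary objective, which opens "To test the hypothesis that that in couples with unexplained or mild male factor infertility". No pilot or feasibility objective is given. Section 8, Step 2, plans a formal chi-square test of live birth without naming a stage. Section 8, Interim Analysis, puts a look after the first 50 participants, on ongoing pregnancy. It lets the DSMC's advice determine whether the study goes on, and leaves the formal stopping rule to a separate SAP.

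**The concern.** Someone who reads Section 3 for the size and length of the trial finds 100 women and 14 months. Someone who reads Section 4.4 finds 966 women and 80% power. Nothing links the two beyond one sentence about a pilot. The plan does not say when the other women are recruited, whether the 100 count toward the 966, or which of the two sizes the test in Section 8 applies to.

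Two things are at stake. If the chi-square test is run on the 100 women as the test of the primary objective, it will say almost nothing about an 8-point difference, and a non-significant result could be misread as no effect. And the DSMC is asked to advise on continuation without being told what would be continued.

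**Working it through.** **Inputs.** Section 4.4: 18% against 26%, two-sided alpha 0.05, 15% loss, 483 per arm. The value .80 is printed as beta but is read here as the power, the only reading that makes sense and the one that reproduces 483. Section 3: 100 women. Equal allocation (50 per arm) is assumed, as in Section 4.4. Section 8: look at 50 women.

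**1. The plan's own figure.** Two-proportion formula with pooled variance under the null hypothesis:

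n = [1.960 × √(2 × 0.22 × 0.78) + 0.842 × √(0.18 × 0.82 + 0.26 × 0.74)]² / 0.08² = 419.7, so 420 per arm.

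420 × 1.15 = 483 per arm, 966 in total. The stated size reproduces.

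**2. Power at 966 after the stated loss.** 483 × 0.85 = 410.55, about 411 per arm rather than 420. Power there is 79.1%. Dividing 420 by 0.85 would have given 495 per arm. The gap of 12 per arm is worth about one point of power.

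**3. Power at the scheduled size.** Power = Φ{[0.08 × √n − 1.960 × √0.3432] / √0.3400}, where 0.3432 = 2 × 0.22 × 0.78 and 0.3400 = 0.1476 + 0.1924.

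- n = 50 per arm: Φ(−1.00) = 15.9%. Exact enumeration of the uncorrected chi-square test gives 16.3%.
- n = 42.5 per arm (15% loss): Φ(−1.07) = 14.1%.
- For 80% power at 50 per arm, the letrozole rate would have to be about 44% against 18%.

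**4. Precision at the scheduled size.** Half-width of the 95% CI for the difference = 1.96 × √(0.3400 / n).

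- n = 50: 16.2 points, full width about 32 points.
- n = 42.5: 17.5 points, full width about 35 points.

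The half-width is thus twice the 8-point target, and the full interval about four times it.

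**5. The look at 50.** 50/100 = 50% of the smaller size; 50/966 = 5.2% of the larger.

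**6. What each section assigns to each size.**

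| Item | 100 women | 966 women |
|---|---|---|
| Trial-level schedule | Section 3 | none |
| Stated power | none | 80%, Section 4.4 |
| Called a pilot | Section 4.4 only | no |
| Chi-square test (Section 8) | not restricted | not restricted |
| What the look at 50 decides | not stated | not stated |
| Whether the 100 count toward the 966 | not stated | not stated |

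**The case against.** The best reply is that Section 4.4 already explains the 100. Read with it, Section 3 is the pilot's timetable and 966 is the size for the hypothesis test. No passage claims 80% power for 100 women, so 16% power matters only if the confirmatory test is applied to them. Section 8 also says that its emphasis is on confidence intervals, and a separate SAP is still to come.

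Much of this stands. A reader might infer that the plan has two rival sample sizes, or that it claims 80% power for 100 women. The documents support neither. What remains is that the label is missing where the size and schedule are stated, that the objective and test are not tied to a stage, and that the 966 have no timetable. The separate SAP can settle the stopping rule and the analysis details, but trial size and schedule belong to Sections 3 and 4.4.

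A reader might also infer that the look at 50 comes too late to affect the pilot. At an even 20 women per month (100 in 5 months), the 50th woman enters at 2.5 months. Section 6.2 says "The study will be completed 4 months after randomisation, with a maximum of 3 cycle attempts", so she finishes at 6.5 months, after the 5 months of inclusion. But this assumes even accrual and a look that waits for outcomes. The interim sentence in Section 8 is unclear and may mean recruitment alone, which puts the look at 2.5 months. A late look could still inform a decision to go on to 966. The argument is therefore not relied on. Nor is an extrapolated duration: 966/20 gives about 48 months of inclusion, but only as an illustration, since no passage says that the pilot's pace would hold.

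**Conclusion.** The point holds as a failure to reconcile sections, not as a flat contradiction. The only scheduled size has about 16% power for 18% against 26% (about 14% after 15% loss), with a 95% CI half-width of about 16 points. The size with about 80% power is not scheduled anywhere. In time order the first 50 women fall within the first 100, but Section 8 leaves open whether going on means to 100 or to 966.

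These figures rest on the rates in Section 4.4, equal allocation and the uncorrected chi-square test. The figure of 966 is not in dispute. The beta label and the 79% power after loss are minor. The point should be fixed, because it governs how any result at 100 women is read and what the DSMC advises on.

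**What to change.** Choose one of two routes.

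**(A) Pilot, then main trial.**

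- In Section 3, label the 100 women and the 14 months as the pilot.
- In Section 8, restrict the confirmatory chi-square test to the 966.
- Give the 966 their own schedule, with follow-up long enough to observe live birth. The 3 months in Section 3 should not be carried forward, since a conception late in the 4-month treatment period cannot reach term within them.
- State what the look at 50 decides, and whether it is taken when 50 are recruited or when 50 have completed their study period.
- State whether pilot women count toward the 966. If they do, the separate SAP must control type I error for any pilot or interim comparison of outcomes.

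**(B) Only 100 women.** State about 16% power for 18% against 26%, and report estimates with 95% CIs in place of a confirmatory test.

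In Section 4.4, under (A), change the label on .80 from beta to power, keep 483 per arm, and state about 79% power after 15% loss.

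**Cost.** The edits are to wording. Route (A) adds no women if the pilot counts; if it does not, the total is 966 + 100 = 1,066. It also brings a longer schedule into the open. Route (B) gives up the hypothesis test in the primary objective. The stated power becomes slightly less favourable.

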6. METHODS

6.1 Study parameters/endpoints

6.1.1 Main study parameter/endpoint

Ongoing pregnancy resulting in live birth, conceived within 3 cycles IUI after randomisation in a time horizon of 4 months. In calculation, we will take the

calculated moment of conception leading to the live birth

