6.1.2 Secondary study parameters/endpoints (if applicable)

- 1. Number of cycles with mono-follicular growth
- 2. Number of cycles with Multiple follicular growth
- 3. Number of cancelled cycles due to the occurrence of >3 follicles >15 mm
- 4. Time to conception leading to live birth
- 5. Clinical pregnancy
- 6. Miscarriage
- 7. Multiple pregnancy (reported as twins and higher order multipl
- 8. PregNANCY COMPLICATIONS
- 9. Direct and indirect costs

Counselling

Women eligible for participation in the study will be invited for additional counselling by a research nurse, to ensure that they are fully informed on the nature of the study by means of written information (Participant Information Form). Women who agree to participate will be asked to sign a written informed consent of which they will receive a copy. Consenting eligible women will be randomly allocated to one of the two strategies at the baseline visit of the first treatment cycle.

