8. STATISTICAL ANALYSIS

Step 1: Summarizing trial data.

Baseline data and outcome data will be separately summarized. For continuous variables, we will examine the distribution of the observations, and if normally distributed then we will summarize them as means with standard deviations (SDs). If they are not normally distributed, then medians and inter-quartile ranges (IRQs) will be reported. For dichotomous data, we will provide proportions (or percentages). In addition to the baseline and outcome data, we will also summarize the recruitment numbers, those lost to follow-up, protocol violations and other relevant data.

Step 2: Inter-group comparisons.

The analysis of all outcomes will be done on an intention to treat basis.

The effectiveness of IUI with letrozole versus IUI in natural cycle will be expressed as a rate ratio for live birth with corresponding 95% confidence intervals. A formal test of the difference in rate will be performed using chi-square test statistics. The effectiveness over time will be evaluated in life tables and differences in live birth over time will be evaluated using the log-rank test. Further dichotomous outcomes will be analyzed using either Fishers Exact Test or chi-square as appropriate. For continuous outcomes we will use t-test if the observations in each trial arm are normally distributed, and if non-normally distributed, then Mann-Whitney-U test will be employed. Although p-values will be reported, the focus will be on providing 95% confidence intervals around point estimates as these are more useful in interpreting the findings of the trial.

Step 3: Adjustments and sensitivity analyses.

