If randomization fails to achieve balanced groups, then we will perform secondary analyses in which we will adjust for unbalanced prognostic factors using procedures such as logistic regression. If the primary unadjusted analysis and secondary adjusted analysis are discordant, we will give greater weighting to the primary analysis in the interpretation of trial findings. For issues such losses to follow-up, missing data, and protocol violations, we will attempt sensitivity ("worst-case scenario") analyses to explore the effect of these factors on the trial findings. As a secondary analysis, we will adjust for missing data using imputation techniques to explore the effects of such imputations on the trial findings. The effect of baseline characteristics on the primary outcome will be explored using logistic regression analysis. In sub analyses the association between follicular growth and live birth will be evaluated.

Details of the analysis will be described in a separate statistical analysis plan, that will be developed during the study, and finalized before data lock.

Interim Analysis

Interim analysis will be done after completion data recruitment of the first 50 participants. An independent Data Safety Monitoring Committee (DSMC) will be invited. The DSMC will be asked to assess the endpoint ongoing pregnancy, as data on live birth will not be available. Also, the DSMC will be provided insight in the SAE's that have occurred. The continuation of the study will depend on the advice of DSMC. A formal stopping rule will be formulated in the separate statistical analysis plan.

Economic evaluation

An economic analysis will be performed alongside the clinical trial. The economic analysis will be performed from a healthcare perspective. Depending on the outcome of live birth rates in both groups, the economic analysis will be a cost-minimization of cost-effectiveness analysis.

Cost-effectiveness of each strategy will be presented as cost per live birth and costs

pre clinical pregnancy. Robustness of the results for various assumptions and parameter estimates will be explored in sensitivity analysis outcomes and will be expressed in ICER graphs and cost-effectiveness acceptability curves. A decision model will be used to evaluate the optimal strategy.

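### The only study calendar stops follow-up at month 13, about 3 to 6 months before the last births, so live birth, the primary endpoint, is incomplete for the 100-woman stage.

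*Combined protocol and SAP*

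**What the plan says.** Section 3 (Study design, time schedule) contains the only calendar in the document. It is written for 100 women, the stage that Section 4.4 introduces with "Firstly we will collect 100 women for a pilot study". It gives a 14-month total: one month of preparation, then "5 months inclusion, 4 months treatment, 3 months follow up and 1 months analysis/report writing".

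Section 6.1.1 defines the primary endpoint as "Ongoing pregnancy resulting in live birth, conceived within 3 cycles IUI after randomisation in a time horizon of 4 months", with the event dated back to the conception that led to the birth. Section 8 (Step 2) states that effectiveness "will be expressed as a rate ratio for live birth with corresponding 95% confidence intervals". Two other outcomes also need the birth: the secondary endpoint "Time to conception leading to live birth" in Section 6.1.2, and the economic evaluation in Section 8, where "Cost-effectiveness of each strategy will be presented as cost per live birth".

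The delay to birth is acknowledged once, for the interim analysis: "The DSMC will be asked to assess the endpoint ongoing pregnancy, as data on live birth will not be available". Three other statements bear on when the study closes, and none of them is tied to delivery:

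- Section 6.2 treats the study as complete 4 months after randomisation.
- Section 10.4 defines the end of study by the final visit of the last participant, without a date.
- Section 8 refers to a separate analysis plan "that will be developed during the study, and finalized before data lock", and the lock has no date.

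**The concern.** Three months after the end of treatment is long enough to confirm an ongoing pregnancy but not to observe a birth. Dating the event to conception does not help, because a conception counts only once it is known to have ended in a live birth.

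If the calendar is followed, too few births are recorded and the live-birth rate is understated in both arms. Time to conception leading to live birth is incomplete for the same reason. Cost per live birth is overstated, because its denominator is short. Complications of late pregnancy are cut off. Section 7.2.2 counts birth defects as serious adverse events, so missed reports of these are a possible further effect, though not a demonstrated one.

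**Working it through.** **Calendar (Section 3).** 1 + 5 + 4 + 3 + 1 = 14 months, so the stated total reproduces. Inclusion runs from month 1 to month 6, treatment ends at month 10, follow-up at month 13 and the report at month 14.

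**Assumptions (not in the documents).**

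- One month is 30.44 days, and enrolment is uniform over months 1–6.
- Conception to birth, g, takes 245 to 266 days (37 to 40 weeks' gestation).
- Cycles last 28 days. Randomisation is on cycle day 3 (Sections 5.1 and 6.1.2) and conception near day 14, so conceptions fall at d = 11, 39 and 67 days after randomisation.
- Conceptions are split equally or 50/30/20 over the three cycles. As a slow extreme, they are spread evenly over the 4 months.

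**Last birth.**

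- Third cycle of the last woman enrolled: 6 + (67 + 266)/30.44 = 16.9 months; with g = 245, 16.2.
- Conception at the end of the window: 10 + 266/30.44 = 18.7 months; with g = 245, 18.0.

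These fall 3.2 to 5.7 months after month 13. At 42 weeks (280 days) the upper figure is month 19.2, a gap of 6.2 months. Even a birth at 28 weeks (182 days) falls after month 13 for these conceptions: month 14.2 for the first case and 16.0 for the second.

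**Share of births by month T.** For a conception at day d, the share is (T − 1 − (d + g)/30.44)/5, limited to 0–1. For example, with T = 13, g = 266 and d = 11, (13 − 1 − 9.10)/5 = 0.580; d = 39 and d = 67 give 0.396 and 0.212. For conceptions spread evenly over 4 months, put s = T − 1 − g/30.44. The share is s²/40 when s ≤ 4 and (s² − (s − 4)²)/40 when 4 < s ≤ 5. With T = 13 and g = 266, 3.26²/40 = 0.266.

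| Conception pattern | Month 13, g = 266 | Month 13, g = 245 | Month 14, g = 266 | Month 14, g = 245 |
|---|---|---|---|---|
| Equal over 3 cycles | 0.396 | 0.534 | 0.596 | 0.734 |
| 50/30/20 | 0.451 | 0.589 | 0.651 | 0.789 |
| Even over 4 months | 0.266 | 0.390 | 0.452 | 0.590 |

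So 27–59% of births occur by month 13. If births were still collected during the reporting month, the share would be 45–79%.

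**Births.** Section 4.4 gives 18% and 26%. It calls them pregnancy rates within a live-birth calculation; they are taken here as live-birth rates, with 50 women per arm.

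- Expected: 50 × 0.18 + 50 × 0.26 = 22.
- Seen by month 13: 22 × 0.266 = 5.9 to 22 × 0.589 = 13.0. Not seen: 9.0 to 16.1.
- With the 15% loss of Section 4.4: 22 × 0.85 = 18.7 expected, 5.0 to 11.0 seen.

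**Scenario in which unobserved births count as failures.** The 18% would appear as 4.8–10.6% and the 26% as 6.9–15.3%. The rate ratio stays at 26/18 = 1.44 when the same share is seen in both arms. Its 95% CI is exp[ln(26/18) ± 1.96 × √((1 − p₁)/(50p₁) + (1 − p₂)/(50p₂))]:

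| Share seen | SE of log ratio | 95% CI |
|---|---|---|
| Complete | 0.385 | 0.68–3.07 |
| 0.589 | 0.528 | 0.51–4.07 |
| 0.266 | 0.817 | 0.29–7.16 |

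**Other reading of the 3 months.** If they run per woman, her follow-up ends 4 + 3 = 7 months after randomisation. The earliest birth at 245 days or later comes at (11 + 245)/30.44 = 8.4 months, or 9.1 months at 266 days. No such birth would be seen.

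**The case against.** The strongest reply is that Section 3 is a one-sentence planning estimate and not a data cut-off. Nothing says that births stop being collected at month 13. The endpoint definition, the undated data lock, and the use of ongoing pregnancy at the interim because live birth is not yet known all suggest authors who meant to wait for deliveries. On that view the calendar is mis-stated and no births would be lost. This part stands: the loss is conditional on the calendar being followed. It does not remove the problem, because no section schedules collection of births beyond month 13, and the substitution of ongoing pregnancy is made for the interim only.

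It can also be said that this is a pilot whose complete-data interval, 0.68–3.07, is already uninformative about efficacy. That is true, but the protocol sets no different primary endpoint for the 100 women.

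The apparent rates and widened intervals are one scenario. The plan does not say that unobserved births count as failures, and Section 8 (Step 3) provides for worst-case analyses and imputation. That caveat stands. However, those tools would here have to stand in for 41–73% of the births, an absence created by the schedule itself.

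Finally, Section 6.2 can be read as giving only the treatment horizon, since it goes on to discuss care after the 4-month period. That reading is reasonable, and a clarification of wording is enough there.

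**Conclusion.** The concern holds, and it must be fixed. As written, the calendar cannot deliver the primary endpoint for the 100-woman stage: follow-up ends 3.2 to 5.7 months before the last births, when only 27–59% of births would have occurred. The exact shares rest on the assumed gestation, cycle timing and uniform enrolment. The existence of the gap does not, since no plausible gestation closes it for the last conceptions.

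The demonstrated harm is understated live-birth rates and lost precision. Bias in the rate ratio is not shown: if time to conception and length of gestation are similar in the arms, its expected value is unchanged. The document gives no calendar for the 966-woman trial, so nothing is concluded about that stage.

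**What to change.** Reconcile Sections 3, 6.1.1, 6.2 and 10.4:

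- **Section 3:** follow every pregnancy conceived in the 4-month window to its outcome. For planning, allow nine months after treatment: 1 + 5 + 4 + 9 + 1 = 20 months in total. This covers the last birth at 266 days (month 18.7). Eight months would miss about 1% of births in the slow extreme: s = 18 − 1 − 8.74 = 8.26, and (9 − 8.26)²/40 = 0.014. A 42-week birth at month 19.2 would fall just beyond nine months, so the outcome rule should govern and not the month count.
- **Section 6.2:** state that 4 months is the treatment and conception horizon.
- **Section 10.4 and Section 8:** define the end of study as the last pregnancy outcome, with data lock and the live-birth analysis after it.

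The alternative is to keep the 14-month report but label it as ongoing pregnancy only, with live birth to follow. Any schedule written for the 966-woman trial should apply the same rule.

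The cost is a protocol amendment and about 5 to 6 more calendar months. No extra patients or procedures are needed; birth outcomes could be collected by telephone or from records.
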